### **Exploratory endpoints**

To examine potential underlying brain mechanisms related to CBD, the proposed study will use MRI to inform the feasibility of incorporating biomarkers (e.g., resting-state functional connectivity) in our future studies and potentially yield testable hypotheses.

During the screening visit, to effectively acclimate the child to the MR environment, we use an MR simulator. Habituating children in an MRI simulator minimizes data loss, which is pivotal for obtaining high-quality longitudinal and pre-/post-intervention brain scans. A Social Story will be read aloud to

prepare the child for the scanning experience. Our team has a long track-record of obtaining high-quality imaging data in neurodevelopmental disorders, including ADHD and autism, with children as young as 5 years old.

Following the mock scan, a scan will be scheduled for the Baseline visit. Imaging will be performed using scanning equipment which have been FDA-approved for clinical and research scans as minimal risk devices. No exogenous contrast agent will be used in any imaging sequence. At the beginning of the scan session, participants will be familiarized with the scanning environment and the research team, while the imaging procedures are being carefully explained. The Social Story will be read aloud again. The research staff will conduct a metal screening interview with the parent(s) to ensure MRI safety and will use a hand-held metal detector to search for any metal on the participant (and the parent, if they plan on entering the scanner suite while the child is being set-up). Additionally, female participants who have begun menstruation will be instructed to take a urine pregnancy test to ensure lack of pregnancy. If there are no contraindications, participants will be brought into the MRI room. The research staff will place earplugs, headphones, pneumatic belt, and finger transducer on the child and have them lay down on the scanner table. The participant will be positioned on their back on the scanner gantry with head straight aligned with the middle of the coil. The radio frequency imaging coil, which obtains the imaging data, will be positioned in front of the child's face. All participants will be asked to limit head motion. Foam padding will be used for comfort and to comfortably restrict head motion. Once the child is comfortable, we will slide the scanner table into the magnet and begin scanning. Between each scan, the child will be in contact with the research staff through a microphone mounted in the MRI scanner. While scanning is on, it gets loud, thus the speaker is turned off and we will not be able to hear the child. This is why the child will have a handheld squeeze-ball device to let the operator know if they wish to immediately stop scanning and be removed from the magnet. Upon being squeezed, the squeeze-ball emits a loud sound in the operator room to notify the research staff who will immediately stop the scan. We spend time during the mock MRI to instruct and coach the child of these procedures so they will be well prepared before the MRI scan.

### 8.3 ADVERSE EVENTS AND SERIOUS ADVERSE EVENTS

#### 8.3.1 DEFINITION OF ADVERSE EVENTS (AE)

Adverse event (AE) means any untoward medical occurrence associated with the use of an intervention in humans, whether or not considered intervention-related (21 CFR 312.32 (a)).

#### 8.3.2 DEFINITION OF SERIOUS ADVERSE EVENTS (SAE)

An AE or suspected adverse reaction is considered "serious" if, in the view of the investigator it results in any of the following outcomes: death, a life-threatening adverse event, inpatient hospitalization or prolongation of existing hospitalization, a persistent or significant incapacity or substantial disruption of the ability to conduct normal life functions, or a congenital anomaly/birth defect. Important medical events that may not result in death, be life-threatening, or require hospitalization may be considered serious when, based upon appropriate medical judgment, they may jeopardize the participant and may require medical or surgical intervention to prevent one of the outcomes listed in this definition. Examples of such medical events include allergic bronchospasm requiring intensive treatment in an emergency room or at home, blood dyscrasias or convulsions that do not result in inpatient hospitalization, or the development of drug dependency or drug abuse.

#### 8.3.3 CLASSIFICATION OF AN ADVERSE EVENT

---

#### 8.3.3.1 SEVERITY OF EVENT

For AEs not included in the protocol defined grading system, the following guidelines will be used to describe severity.

- **Mild** – Events require minimal or no treatment and do not interfere with the participant’s daily activities.
- **Moderate** – Events result in a low level of inconvenience or concern with the therapeutic measures. Moderate events may cause some interference with functioning.
- **Severe** – Events interrupt a participant’s usual daily activity and may require systemic drug therapy or other treatment. Severe events are usually potentially life-threatening or incapacitating. Of note, the term “severe” does not necessarily equate to “serious”.

---

#### 8.3.3.2 RELATIONSHIP TO STUDY INTERVENTION

All AEs must have their relationship to study intervention assessed by the clinician who examines and evaluates the participant based on temporal relationship and his/her clinical judgment. The degree of certainty about causality will be graded using the categories below. In a clinical trial, the study product must always be suspect.

- **Related** – The AE is known to occur with the study intervention, there is a reasonable possibility that the study intervention caused the AE, or there is a temporal relationship between the study intervention and event. Reasonable possibility means that there is evidence to suggest a causal relationship between the study intervention and the AE.
- **Not Related** – There is not a reasonable possibility that the administration of the study intervention caused the event, there is no temporal relationship between the study intervention and event onset, or an alternate etiology has been established.

---

#### 8.3.3.3 EXPECTEDNESS

The PI will be responsible for determining whether an AE was expected or unexpected. An AE will be considered unexpected if the nature, severity, or frequency of the event is not consistent with the risk information previously described for the study intervention.

---

#### 8.3.4 TIME PERIOD AND FREQUENCY FOR EVENT ASSESSMENT AND FOLLOW-UP

The occurrence of an AE or SAE may come to the attention of study personnel during study visits and interviews of a study participant presenting for medical care.

All AEs including local and systemic reactions not meeting the criteria for SAEs will be captured on the appropriate case report form (CRF). Information to be collected includes event description, time of onset, clinician’s assessment of severity, relationship to study product (assessed only by those with the training and authority to make a diagnosis), and time of resolution/stabilization of the event. All AEs occurring while on study must be documented appropriately regardless of relationship. All AEs will be followed to adequate resolution.

Any medical condition that is present at the time that the participant is screened will be considered as baseline and not reported as an AE. However, if the study participant’s condition deteriorates at any time during the study, it will be recorded as an AE.

Changes in the severity of an AE will be documented to allow an assessment of the duration of the event at each level of severity to be performed. AEs characterized as intermittent require documentation of onset and duration of each episode.

The PI will record all reportable events with start dates occurring any time after informed consent is obtained until 7 (for non-serious AEs) or 30 days (for SAEs) after the last day of study participation. At each study visit, the investigator will inquire about the occurrence of AE/SAEs since the last visit. Events will be followed for outcome information until resolution or stabilization.

---

#### 8.3.5 ADVERSE EVENT REPORTING

The study clinician will immediately report to the IRB any adverse event, whether or not considered study intervention related, including those listed in the protocol or investigator brochure and must include an assessment of whether there is a reasonable possibility that the study intervention caused the event. Disease related events (DRE), such as behavioral disruptions (e.g., tantrums) will not be reported as AE, unless their severity or frequency far surpasses their prior levels.

All AEs will be followed until satisfactory resolution or until the site investigator deems the event to be chronic or the participant is stable.

The investigator will be responsible for notifying the FDA of any unexpected or suspected severe adverse reaction as soon as possible, but in no case later than 7 calendar days after the investigator's initial receipt of the information. In addition, the investigator must notify FDA and all participating investigators in an Investigational New Drug (IND) safety report of potential serious risks, from clinical trials or any other source, as soon as possible, but in no case later than 15 calendar days after the investigator determines that the information qualifies for reporting.

---

#### 8.3.6 SERIOUS ADVERSE EVENT REPORTING

The study clinician will immediately report to the IRB any serious adverse event, whether or not considered study intervention related, including those listed in the protocol and must include an assessment of whether there is a reasonable possibility that the study intervention caused the event.

All SAEs will be followed until satisfactory resolution or until the site investigator deems the event to be chronic or the participant is stable.

The investigator will be responsible for notifying the FDA of any unexpected fatal or life-threatening suspected adverse reaction as soon as possible, but in no case later than 7 calendar days after the investigator's initial receipt of the information. In addition, the investigator must notify FDA and all participating investigators in an IND safety report of potential serious risks, from clinical trials or any other source, as soon as possible, but in no case later than 15 calendar days after the investigator determines that the information qualifies for reporting.

---

#### 8.3.7 REPORTING EVENTS TO PARTICIPANTS

Parents/guardians will be informed about AEs and SAEs, and study-related results on an individual level. Similarly, parents/guardians will be informed of incidental findings that may emerge from study procedures. A summary of study participation will be provided at the conclusion of each participant's treatment, including any incidental findings of clinical relevance. Parents/guardians will be given the opportunity to discuss any such results directly with the investigational team.

---

### 8.3.8 EVENTS OF SPECIAL INTEREST

Not applicable.

---

### 8.3.9 REPORTING OF PREGNANCY

Because risks of CBD use in pregnancy are unknown, all participants are required to use abstinence or use a valid method of contraception to participate in the study. Menstruating females will undergo urine pregnancy tests at the screening visit to ensure participant safety. If a participant becomes pregnant during the study, she will immediately be discontinued from the medication. Participants who become pregnant during the study, or within 30 days after completing the study, will be followed throughout the course of the pregnancy for safety, with the participant's permission and that of her parent/guardian. Information about the risks of the pregnancy and the possible effects on the fetus will be provided to support an informed decision in cooperation with the treating physician and the obstetrician. Any spontaneous abortion will be classified as a serious adverse event. Pregnancy of a participant will be reported to study leadership and the IRB.

---

## 8.4 UNANTICIPATED PROBLEMS

---

### 8.4.1 DEFINITION OF UNANTICIPATED PROBLEMS (UP)

The Office for Human Research Protections (OHRP) considers unanticipated problems (UP) involving risks to participants or others to include, in general, any incident, experience, or outcome that meets **all** of the following criteria:

- Unexpected in terms of nature, severity, or frequency given (a) the research procedures that are described in the protocol-related documents, such as the IRB-approved research protocol and informed consent document; and (b) the characteristics of the participant population being studied;
- Related or possibly related to participation in the research ("possibly related" means there is a reasonable possibility that the incident, experience, or outcome may have been caused by the procedures involved in the research); and
- Suggests that the research places participants or others at a greater risk of harm (including physical, psychological, economic, or social harm) than was previously known or recognized.

---

### 8.4.2 UNANTICIPATED PROBLEM REPORTING

The investigator will report UPs to the reviewing IRB. The UP report will include the following information:

- Protocol identifying information: protocol title and number, PI's name, and the IRB project number;
- A detailed description of the event, incident, experience, or outcome;
- An explanation of the basis for determining that the event, incident, experience, or outcome represents an UP;
- A description of any changes to the protocol or other corrective actions that have been taken or are proposed in response to the UP.

To satisfy the requirement for prompt reporting, UPs will be reported using the following timeline:

- UPs that are SAEs will be reported to the IRB within 7 calendar days of the investigator becoming aware of the event.
- Any other UP will be reported to the IRB within 14 days of the investigator becoming aware of the problem.
- All UPs should be reported to appropriate institutional officials (as required by an institution's written reporting procedures), the supporting agency head (or designee), and the OHRP within 30 days of the IRB's receipt of the report of the problem from the investigator.

---

#### 8.4.3 REPORTING UNANTICIPATED PROBLEMS TO PARTICIPANTS

Parents/guardians will be informed any UPs on an individual level. Parents/guardians will be given the opportunity to discuss any concerns regarding UPs directly with the investigational team.

## 9 STATISTICAL CONSIDERATIONS

### 9.1 STATISTICAL HYPOTHESES

The hypothesis of this phase 2 open trial is that moderate doses of CBD may be therapeutically beneficial for core and/or associated symptoms in children and adolescents with ASD.

### 9.2 SAMPLE SIZE DETERMINATION

No statistical methods were used to determine the sample size for this study. The total number of participants expected to participate at NYU Child Study Center and Comprehensive Epilepsy Center is 30.

### 9.3 POPULATIONS FOR ANALYSES

Participants included within the analysis datasets include all participants in the trial, including both responders and non-responders, to examine efficacy at varying doses as well as safety and tolerability across the whole sample.

### 9.4 STATISTICAL ANALYSES

---

#### 9.4.1 GENERAL APPROACH

The primary aim of this study is to determine the optimal dose of CBD in children and adolescents with ASD. Therefore, to increase sensitivity in capturing a nonlinear dose response, we will employ the BOIN design as discussed above. After the trial is completed, we will select the optimal dose based on isotonic regression as specified in Liu and Yuan (66).

---

#### 9.4.2 ANALYSIS OF THE PRIMARY EFFICACY ENDPOINT(S)

We will select as the optimal dose the dose for which the isotonic estimate of the response rate is closest to the target response rate. If there are ties, we will select the higher dose level when the isotonic estimate is lower than the target response rate and we will select the lower dose level when the isotonic estimate is greater than or equal to the target response rate.

As mentioned, response rate will be determined by the proportion of participants classified as responders. A treatment response is defined as a CGI-I score of 1 or 2 on the individualized, predetermined primary outcome variable, whereas a nonresponse is a CGI-I score of 3 or greater. Scores on the CGI-I will be determined by clinician consensus.

Table 5 shows the operating characteristics of a 5-dose BOIN design based on 1000 simulations. The operating characteristics show that the design selects the true optimal dose, if any, with high probability and allocates more participants to the dose levels with the response rate closest to the target of 0.6. Please refer to Tables 3 and 4 for the design and statistical expectations relevant to Part 2 of the study.

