Of note, there is limited data available to suggest most promising dosage and there is preliminary research evidence suggesting the possibility of nonlinearity in the dose response across a variety of outcomes (2, 9). Determining the optimal dose of CBD is essential in maximizing potential for treatment of core and associated ASD symptoms. Therefore, we will evaluate varying dose levels by implementing an adaptive design to determine at which dose the largest proportion of participants respond. The definition of treatment response will be individualized for each participant based upon a predetermined target symptom cluster that is considered most interfering at study outset. Lastly, we also intend to collect brain MRI data before and after open CBD treatment to provide insights into feasibility of incorporating biomarkers into subsequent studies, and potentially yield testable hypotheses.

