### 3 OBJECTIVES AND ENDPOINTS

OBJECTIVES	ENDPOINTS	JUSTIFICATION FOR ENDPOINTS
Primary		
Determine the optimal dose of CBD in children and adolescents with ASD	Establishment of optimal dose of CBD in children and adolescents with ASD, defined as the dose at which the greatest proportion of participants respond. Discussed further in the Dosing and Administration section, the definition of treatment response will be individualized for each participant based upon a predetermined target symptom cluster.	Identification of the optimal dose of CBD (within the range tested) is desirable given the insufficient research in this area and the potential for dose-dependent inverted-U effects (2, 9).
Secondary		
Identify the primary outcome measure for a subsequent double-blind placebo-controlled RCT	Change in core and associated symptoms from baseline based upon measures developed to assess ASD symptoms, symptoms often associated with ASD, and global functioning including: 
 
- ABC Social Withdrawal and Irritability Subscales
 
- ASC-ASD-Child and Parent
 
- AFEQ
 
- ADAMS
 
- BIS
 
- CGI-I
 
- CGI-S
 
- HSQ-ASD
 
- OSU Autism CGI Severity
 
- OSU Autism CGI Improvement
 
- RBS-R
 
- SCARED
 
- SDSC
 
- SRS-2
 
- SWAN (Part 2 of the trial)
 
- Vineland-3
 
	Measures were selected because they have been widely used in prior trials in ASD (ABC, CGI, HSQ-ASD, OSU Autism CGI, RBS-R, SCARED, SRS-2, SWAN [Part 2], Vineland-3), or have been used in a recent trial of CBD in Fragile X syndrome (ADAMS) or have been used in medication trials more broadly (SDSC), or represent new and innovative tools available in the ASD field (ASC-ASD; AFEQ; BIS).
Tertiary/Exploratory		
Assess underlying brain mechanisms using MRI	Change in brain activity, indexed by resting-state functional connectivity. Otherwise, results will be reported	Inform the feasibility of incorporating biomarkers (e.g., resting-state functional

OBJECTIVES	ENDPOINTS	JUSTIFICATION FOR ENDPOINTS
	qualitatively (conducted at in-person visits only, if participants agree)	connectivity) in our future studies and potentially yield testable hypotheses.

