    - Non-response: no-to-minimal therapeutic benefit captured by a CGI-I score of 3 (minimally improved) or greater (i.e., no change or any worsening) determined by consensus as indicated above, and/or severe AE, defined as severe cognitive or behavioral toxicity, impaired liver and renal function, or impaired hematopoiesis that is deemed to be potentially or likely related to study medication (also see section 8.3.2), causing early discontinuation of study intervention.

While applying a uniform statistically derived algorithm for defining treatment response and non-response for all patients would have been preferable, the above procedures were implemented given the exploratory nature of the study and the wide range of therapeutic effects that CBD may exert. The intent of this exploratory study has been to provide the foundation for a well-defined subsequent RCT.

Over the first 15 participants, we have identified five as responders, for an overall response rate of 33%, and a response rate of  $4/9 = 44\%$  on 6 mg/kg/day, as opposed to the 60% rate anticipated on the optimal dose. The response rate on 3 mg/kg/day was  $1/6 = 16\%$ . Per the BOIN design that we implemented, we have excluded both the 6 mg/kg/day and 3 mg/kg/day dose for further testing. We believe that it would be scientifically valuable to test the 9 mg/kg/day dose on the remaining 15 participants that were originally approved for this open trial. The purpose would be to further confirm the overall safety of the AE profile – which is likely given the pediatric experience with 10 mg/kg/day and 20 mg/kg/day in patients with refractory epilepsy who are more medically fragile. It has also been hypothesized that higher doses of CBD may have preferential effects on D2high receptors in the striatum. If so, that might explain why all five responders had ASD, as well as ADHD.

Accordingly, we now request that we amend the open trial to test only the dose of 9 mg/kg/day and that we require the combination of ASD and ADHD for inclusion. All other aspects of the trial would be unchanged, other than adding the Strengths and Weaknesses of Attention-Deficit/Hyperactivity Disorder Symptoms and Normal Behavior (SWAN) as a dimensional measure of ADHD and completing the K-SADS-COMP at the screening visit rather than the baseline/enrollment visit so that the study clinicians can confirm the presence of an ADHD diagnosis.

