Given our experience with the first 15 participants, we anticipate that at least 1/3 will be classified as responders. If none of the first 6 participants on 9 mg/kg/day are responders, then we would eliminate the dose and terminate the trial. A low, non-zero response rate, as shown below in Table 3, would also determine terminating the trial, as it would be tantamount to evidence that the optimal dose was 6 mg/kg/day, our initial starting dose.

**Table 3.** Dose elimination rules for cohorts 6 to 10

Cohort	1	2	3	4	5	6	7	8	9	10
Number of participants to be treated at the current dose	3	6	9	12	15	18	21	24	27	30
Dose administered (mg/kg/d)	6	6	3	3	6	9	9	9	9	9
Cumulative N of respondents	1	3	4	4	5	-	-	-	-	-
Terminate if # of responses <=						NA	5	6	7	

Thus, we propose to enroll at least six more participants on the dose of 9 mg/kg/day. If none of them respond, the cumulative number of respondents would remain 5, and we will discontinue the trial; if at least 1 responds within the first 6, we will enroll 3 additional participants. If the total number of responders remains 6, we will discontinue the trial. If the number of responders is 7 or more after 9 participants are enrolled, we will enroll an additional 3 participants for a total of 12 on this dose. If the number of responders does not increase beyond a total of 7, we will terminate due to likely futility.

Table 4 provides the operating characteristics of this design extension for a variety of true response rates.

**Table 4.** Operating characteristics of 9 mg/kg/day evaluation

	Dose 1	Dose 2	Dose 3	Dose 4	Dose 5
True response rate	0.1	0.2	0.3	0.4	0.5
Probability of early termination(%)	90.4	60.8	31.0	11.9	3.5

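### The final dose-selection rule (isotonic estimate closest to 0.60) contradicts the primary endpoint (dose with the greatest proportion of responders) and names a different dose over much of the plausible range

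*Combined protocol and SAP*

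**What the plan says.** Section 3 sets the primary endpoint as the optimal dose, "defined as the dose at which the greatest proportion of participants respond". The Synopsis (Section 1.1) says the same, and Section 2.1 describes the adaptive design as a means "to determine at which dose the largest proportion of participants respond".

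Section 9.4.1 gives a different route: "After the trial is completed, we will select the optimal dose based on isotonic regression". Section 9.4.2 then picks "the dose for which the isotonic estimate of the response rate is closest to the target response rate". The target is 0.60 (Sections 6.1.2 and 9.4.2). For ties, "we will select the higher dose level when the isotonic estimate is lower than the target response rate".

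Section 6.1.2 adds three statements that bear on the choice. Of the Part 1 doses, it says "we have excluded both the 6 mg/kg/day and 3 mg/kg/day dose for further testing". For Part 2 on 9 mg/kg/day, "we anticipate that at least 1/3 will be classified as responders". And if the response on 9 mg/kg/day is low, "it would be tantamount to evidence that the optimal dose was 6 mg/kg/day, our initial starting dose".

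**The concern.** Closest to target is a natural rule for a quantity that should not be exceeded, such as a toxicity rate. Applied to benefit, it penalises a dose for working better than 60%. The isotonic step brings a second problem. It forces response to be non-decreasing in dose, whereas Sections 2.2, 3 and 4.1 motivate the study by a possible inverted-U or non-linear curve. If the highest dose does worse than the middle one, the fit cannot show it: it averages the two, and the tie rule then passes the choice to the higher dose.

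This is the decision rule for the primary objective, and its result feeds the planned placebo-controlled trial. With two incompatible rules in the protocol, either dose could be reported as optimal after open-label data have been seen.

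**Working it through.** **Inputs.** Part 1: 1/6 on 3 mg/kg/day and 4/9 on 6 mg/kg/day (Sections 4.2 and 6.1.2). Part 2: up to 15 participants on 9 mg/kg/day (Section 4.3), stopping at 0/6, at most 1/9, or at most 2/12. Those limits are Table 3's cumulative counts of 5, 6 and 7 less the 5 responders from Part 1. Target 0.60.

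**Reproducing the plan's figure.** Exact sequential binomial probability of early termination under those stops, against Table 4:

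| True rate | 0.1 | 0.2 | 0.3 | 0.4 | 0.5 |
|---|---|---|---|---|---|
| Table 4 (%) | 90.4 | 60.8 | 31.0 | 11.9 | 3.5 |
| Recomputed (%) | 90.5 | 60.5 | 30.5 | 11.9 | 3.5 |

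The agreement shows that the stopping rule is read as intended.

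**Selection at n = 15.** I fitted a non-decreasing isotonic regression weighted by n (pool-adjacent-violators) to 1/6, 4/9 and x/15, took the dose closest to 0.60 with the Section 9.4.2 tie rule, and compared it with the highest observed proportion.

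- x = 5: 5/15 = 0.333 is below 4/9 = 0.444, so the two doses pool to (4+5)/(9+15) = 9/24 = 0.375. They tie below 0.60, so 9 mg/kg/day is selected (33% against 44%).
- x = 11: |0.733 − 0.60| = 0.133 is less than |0.444 − 0.60| = 0.156, so 9 mg/kg/day is selected.
- x = 12: |0.800 − 0.60| = 0.200 exceeds 0.156, so 6 mg/kg/day is selected (44% against 80%).

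| Responders on 9 mg/kg/day | Section 9.4.2 selects | Greatest proportion | Agree? |
|---|---|---|---|
| 3/15 to 6/15 (case a) | 9 mg/kg/day | 6 mg/kg/day | No |
| 7/15 to 11/15 | 9 mg/kg/day | 9 mg/kg/day | Yes |
| 12/15 to 15/15 (case b) | 6 mg/kg/day | 9 mg/kg/day | No |

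Fewer than 3/15 cannot occur, because Table 3 would already have stopped the trial. Smoothing the proportions as (y + 0.05)/(n + 0.1) changes no selection.

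**Early stops.** At 0/6, 1/9 and 2/12 the pooled values are 4/15 = 0.267, 5/18 = 0.278 and 6/21 = 0.286. Read literally, Section 9.4.2 names 9 mg/kg/day each time, while Section 6.1.2 eliminates that dose or points to 6 mg/kg/day.

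**Chance of disagreement.** Exact probabilities, counting only trials that reach n = 15 (early stops are taken to follow Section 6.1.2):

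| True rate on 9 mg/kg/day | 0.3 | 0.333 | 0.4 | 0.5 | 0.6 | 0.7 | 0.8 |
|---|---|---|---|---|---|---|---|
| Disagreement (%) | 56 | 57 | 49 | 29 | 18 | 31 | 65 |

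At 1/3 nearly all of this is case (a). At 0.6 it is 9% case (a) and 9% case (b). At 0.8 it is almost all case (b). If early stops also counted as disagreement, the figure at 1/3 would be about 80%.

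**The case against.** **Scope.** The strongest reply is that Section 9.4.2 covers Part 1 only. The isotonic text sits with the BOIN design, the Synopsis places Part 2 after that design is complete, Table 5 is labelled Part 1, and Section 9.4.2 refers the reader to Tables 3 and 4 for Part 2. On Part 1 data alone the rules agree: 4/9 is both the highest proportion and the closest to 0.60. But Section 9.4.1 applies the selection once the trial is completed, without that limit. If the limit was intended, nothing chooses among the doses when Part 2 runs to 15, because Table 3 only terminates. Either reading needs a correction.

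**Table 2.** If its elimination limit of 5 or fewer out of 15 carried into Part 2, 3/15 to 5/15 would no longer conflict, and disagreement would fall to about 17% at a true rate of 1/3 and 20% at 0.4. However, Table 3 is the rule given for cohorts 6 to 10, and 6/15 and 12/15 or more would still conflict.

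**Candidacy.** Case (b) needs 6 mg/kg/day to remain selectable. The protocol excludes it only from further testing and still allows it to be called optimal. If it were barred, case (b) would vanish and case (a) would remain. Case (b) is also unlikely at modest true rates: about 0.03% at 1/3, 0.2% at 0.4 and 1.8% at 0.5.

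**Early stops.** It is fair to say that the specific text in Section 6.1.2 handles these outcomes, which is why they are left out of the main probabilities.

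**Exploratory status.** Section 4.1 calls all endpoints exploratory, and individual data will be listed, so response by dose stays visible. The named optimal dose is nonetheless the study's main output.

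**Conclusion.** The concern holds and must be fixed. Followed literally, the selection rule can name a dose that fails the trial's own definition of optimal, including at 5/15, exactly the 1/3 the plan anticipates as a minimum. For trials reaching 15 on 9 mg/kg/day, the two rules agree only at 7/15 to 11/15, and the chance of disagreement runs from 18% to 65% over true rates of 0.3 to 0.8.

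These figures assume an isotonic fit that increases with dose and is weighted by n, 6 mg/kg/day as a continuing candidate, and Table 3 as the operative stopping rule. The conclusion that the text needs correcting does not depend on them, since a Part-1-only reading leaves Part 2 without a final rule. Nothing here says which dose is right.

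**What to change.** Rewrite Sections 9.4.1 and 9.4.2 so that the final selection follows the endpoint. Suggested text:

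> After the trial is completed, the response proportion at each candidate dose will be estimated separately, with an exact 95% confidence interval and no assumption that response is monotone in dose. The optimal dose is the candidate dose with the highest estimated proportion. Doses with equal proportions will be reported as tied.

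Then:

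- Remove the closest-to-target, isotonic and tie-break text from the final selection, and keep 0.60 only as the Part 1 escalation target.
- State which doses are candidates, and reconcile this with Section 6.1.2, which excludes 3 and 6 mg/kg/day from further testing, may still name 6 mg/kg/day optimal, and sets the Table 3 stops.
- State that comparing 9 mg/kg/day with the lower doses is confounded, because Part 2 requires ADHD and Part 1 did not. Any ranking is therefore descriptive.
- Record the date of the change and that it followed sight of Part 1, and possibly some Part 2, open-label data (the Summary of Changes reports analyses at n = 19).

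The cost is wording only, with no new data, visits or participants. There are two downsides. It is a data-informed change to the primary rule and must be reported as such. And no strength is borrowed across doses, so intervals are wide: exact 95% limits are 0.4–64% for 1/6, 14–79% for 4/9, 12–62% for 5/15 and 52–96% for 12/15. The tie sentence is only a safeguard. No Table 3 end point (0/6, 1/9, 2/12 or x/15) equals 4/9, so a tie with 6 mg/kg/day could arise only on an unplanned closure, for example at 4/9.
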